#### Table 5: Assignments for Progression and Censoring Dates for PFS Analysis

Situation	Date of Event (Progression/Death) or Censoring	Outcome Event (Progression/Death) Or Censored
Progression documented between scheduled visits	Date of assessment of progression 	Event
No progression (or death)	Date of last 'adequate' assessment of response 	Censored
New anticancer treatment started (prior to documented disease progression). 	Date of last 'adequate' assessment of response  (on or prior to starting anti-cancer therapy)	Censored
Death without PD	Date of death	Event

 The earliest of (i) Date of radiological assessment showing new lesion (if progression is based on new lesion); or (ii) Date of radiological assessment showing unequivocal progression in non-target lesions, or (iii) Date of last radiological assessment of target lesions (if progression is based on increase in sum of target lesions)

- 2. An adequate assessment is defined as an assessment where the Investigator] determined response is CR, PR, or SD.
- 3. If PD and New anti-cancer therapy occur on the same day assume the progression was documented first e.g., outcome is progression and the date is the date of the assessment of progression). If anti-cancer therapy is started prior to any post-baseline adequate assessments, censoring date should be the treatment start date.

PFS will be summarized using a Kaplan-Meier survival curve. The Kaplan-Meier estimate for the median progression-free survival time and the first and third quartiles will be presented, along with a naive approximate 90% confidence interval if there are a sufficient number of progressions or deaths. This analysis will be repeated on the mITT population as a supportive analysis of PFS.

#### **Overall Survival (OS)**

Overall Survival (OS) is defined as the time from the first dose of the study medication until death due to any cause. The length of this interval is calculated as the date of death minus the date of treatment start plus one. Subjects who have not died at the time of the analyses will be censored at the date of last contact (as recorded in the eCRF). Last date of contact will be defined as the maximum date of any visit date or the survival follow-up date. Only subject contacts recorded in the eCRF can be used for the calculation of last date of contact.

OS will be summarized using Kaplan-Meier survival curves. The Kaplan-Meier estimate for the median OS time and the first and third quartiles will be presented, along with a naïve approximate 90% confidence interval if there are a sufficient number of deaths.

#### **Clinical Benefit**

This is defined as the percentage of subjects achieving either a complete or partial tumor response or stable disease for at least two protocol scheduled disease assessments as per RECIST criteria. 90% confidence intervals will be produced to characterize the variability around the point estimate. Supportive analyses will be done using the mITT and PP populations.

#### Time to Progression (TTP)

Time to Progression (TTP) is defined as the interval between the date of of first dose of protocol therapy and the earliest date of disease progression or death due to disease under study. Subjects are considered to have progressive disease if they have documented progression based on radiologic assessment as determined by investigator review.

The data structure on how to assign the event and censoring to a subject is same as that defined in the Table 5 under PFS analysis. TTP will be calculated as the date of event/censoring minus the date of first protocol therapy for each subject plus one.

TTP will be summarized using a Kaplan-Meier survival curve. The Kaplan-Meier estimate for the median time to progression and the first and third quartiles will be presented, along with a naive approximate 90% confidence interval if there are a sufficient number of events.

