### 2. Study Objectives and Endpoints

3. Ewing sarcoma/peripheral Primitive Neuro Ectodermal Tumor (PNET).	
Secondary	
• To determine the investigator assessed objective response rate of pazopanib in children, adolescents, and young adults (subjects) with relapsed or refractory solid tumors of the following types (each defining a cohort):	• Objective Response Rate (ORR) for the four tumor types of secondary interest. The analysis method will be the same as in the primary endpoint.
1. osteosarcoma,	
2. neuroblastoma (measurable),	
3. neuroblastoma (evaluable), or	
4. hepatoblastoma.	
• To further define and describe the toxicities of oral pazopanib in subjects with recurrent/refractory solid tumors.	• Adverse Events, Clinical Laboratory Evaluations, Vital signs and ECG and ECHO/MUGA.
• To further characterize the pharmacokinetics (PK) of pazopanib after administration of the powder suspension formulation in children, adolescents and young adults with cancer.	• Pazopanib PK parameters (e.g., Cmax, Tmax, and AUC).
• To determine progression free survival in subjects with relapsed or refractory solid tumors, per cohort.	• Progression-free survival (PFS): defined as the interval between the date of first dose of protocol therapy and the earliest date of disease progression or death due to any cause.
• To determine the time to progression in subjects with relapsed or refractory solid tumors, per cohort.	• Time to progression (TTP): defined as the interval between the date of first dose of protocol therapy and the earliest date of disease

	progression or death due to disease under study.
• To determine the therapeutic activity (a confirmed complete or partial response based on the disease assessment at least one cycle after initial response or stable disease for at least two protocol scheduled disease assessments as per RECIST criteria) per cohort	• Clinical Benefit: defined as the percentage of subjects achieving either a confirmed complete or partial tumor response (at least one cycle after initial response, see section 10.1 for confirmation of CR/PR) or stable disease for at least two protocol scheduled disease assessments as per RECIST criteria.
• To further examine the biologic relationship between tumor response and angiogenic cytokines.	• To be described in a separate biomarker analysis plan.

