Situation	Date of Event (Progression/Death) or Censoring	Outcome Event (Progression/Death) Or Censored
No (or inadequate) baseline tumor assessments	Treatment start date	Censored
No post-baseline assessments and the subject has not died (if the subject has died follow the rules for death indicted at the bottom of the table)	Treatment study date	Censored

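### The SAP's TTP definition counts only disease deaths, but its event rule is PFS Table 5, where any death without progression is an event

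*SAP*

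**What the plan says.** **Definitions.** SAP Section 2 ends the PFS interval at "the earliest date of disease progression or death due to any cause". It ends the TTP interval at "progression or death due to disease under study". Cause of death is the only difference between the two. SAP 10.2 repeats the TTP definition ("the earliest date of disease progression or death due to disease under study"), and the TTP text in protocol 9.8.2.5 agrees. The protocol leaves the assignment of event and censoring times to the RAP, which is this SAP.

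**Assignment rule.** For TTP, SAP 10.2 gives one rule: "The data structure on how to assign the event and censoring to a subject is same as that defined in the Table 5 under PFS".

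**Table 5.** The last row, "Death without PD", is an event at the date of death and sets no condition on cause. The row for subjects with no post-baseline assessment sends those who died to that same row. The PFS text above the table says that on-study deaths of any cause are included. Subjects with neither progression nor death are censored at "Date of last 'adequate' assessment of response". There is no TTP row, footnote or exception.

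**The concern.** The definition and the assignment rule cannot both be followed for a subject who dies of something other than the tumour without documented progression. The definition says there is no TTP event; Table 5 says there is one, at the date of death.

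A programmer working from Table 5 would produce a TTP variable with the same status and date as PFS for every subject. Protocol objective 1.2.5 (TTP) would then have no analysis distinct from objective 1.2.4 (PFS). Any death from another cause would pull the TTP curve down. The plan does expect such deaths to be possible: SAP 11.4 summarizes treatment-related fatal SAEs and primary cause of death.

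**Working it through.** The plan states no figure for this point, so there is none to reproduce. The check is to apply both rules to the same subjects.

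**Step 1: where the rules differ.** Cross adequate baseline (yes/no), new anti-cancer therapy (yes/no), documented PD on or before any new therapy (yes/no) and death (none/disease/other cause): 2 × 2 × 2 × 3 = 24 combinations. The baseline and new-therapy rows are taken to override the death row, as the PFS text implies.

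- No adequate baseline (12 combinations): censored at treatment start under both rules.
- Adequate baseline, new therapy (6): handled by the same rows under both rules.
- Adequate baseline, no new therapy, PD (3): event at PD under both.
- Adequate baseline, no new therapy, no PD (3): alive is censored under both; disease death is an event under both; death from another cause **differs**.

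So the rules differ in 1 of 24. This locates the defect; it is not a frequency.

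**Step 2: single-subject examples (assumed days).**

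| Subject | Table 5 | TTP definition |
|---|---|---|
| Last adequate scan day 56, other-cause death day 90 | event, day 90 | censored, day 56 |
| No post-baseline scan, other-cause death day 30 | event, day 30 | censored, treatment start |

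**Step 3: effect on the Kaplan-Meier curve.** Let k be the number of such deaths in a cohort of n.

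(a) *All k deaths precede every progression and other censoring.* Table 5 multiplies the curve by (n − k)/n at the deaths. Under the definition these subjects leave at treatment start. Later risk sets are the same, so afterwards S(Table 5) = (1 − k/n) × S(TTP).

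(b) *The deaths come later, with r subjects at risk and no progression between the last assessment and death.* The factor is (1 − k/r).

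The cohort sizes 10 and 20 come from the two-stage design. The documents do not give k; 0 to 2 is assumed. Illustrative times: 40% of n progress at week 8, 20% at week 16, the rest are censored at week 28. Deaths are at week 4 in (a), and at week 12 with last assessment at week 8 in (b).

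| Case | Table 5 | TTP definition | Ratio |
|---|---|---|---|
| (a) n=10, k=1, S(8) | 0.9 × 5/9 = 0.500 | 5/9 = 0.556 | 0.90 |
| (a) n=10, k=2, S(8) | 0.8 × 4/8 = 0.400 | 4/8 = 0.500 | 0.80 |
| (a) n=20, k=1, S(8) | 0.95 × 11/19 = 0.550 | 11/19 = 0.579 | 0.95 |
| (a) n=20, k=2, S(8) | 0.9 × 10/18 = 0.500 | 10/18 = 0.556 | 0.90 |
| (b) n=10, k=1, r=6, S(12) | 0.6 × 5/6 = 0.500 | 0.600 | 0.83 |
| (b) n=20, k=1, r=12, S(12) | 0.6 × 11/12 = 0.550 | 0.600 | 0.92 |

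With k = 0 the curves are identical.

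**The case against.** **The reference to Table 5 may mean layout only.** The table is headed for PFS, and the TTP paragraph restates its own definition first. If the definition governs, a death from another cause is not an event, and the table's no-progression row could supply the censoring date. That is a possible intention, but the sentence says the table governs how events and censoring are assigned, and nothing sets the death row aside. What stands is that a short clarification is enough.

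**Separate dataset specifications may already contain the cause condition.** SAP 9.2 says such specifications hold full derivation details. They are not among the documents, so this cannot be ruled out. It would not remove the contradiction in the SAP, where the protocol places these rules.

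**The early-death figures depend on an unsettled point in the PFS section.** The PFS text censors subjects without an adequate post-baseline assessment at treatment start and makes no exception for death; Table 5 sends those who died to the death row. Under the text, the deaths in case (a) would not be events even for PFS, and the difference would vanish. TTP borrows the table rather than the text, so case (a) follows from the rule as referenced. Case (b) does not depend on this.

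**Little rides on TTP.** No hypothesis is tested on it, the study was declared futile after stage 1 (SAP 4.3), and SAP 9.1 lets the team review which analyses remain appropriate on termination. This stands as a limit on importance. SAP 4.4 still plans an end-of-study analysis with cumulative efficacy data, and TTP remains in the SAP.

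**Conclusion.** The concern holds. The TTP definition and the TTP assignment rule contradict each other, and the rule as written misclassifies one kind of subject: adequate baseline, no new anti-cancer therapy, no documented progression, and death from a cause other than the disease under study.

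The size depends on the number of such deaths, which the documents do not give. On the assumed range of 0 to 2, the Table 5 curve is 0.80 to 0.90 of the correct one for n = 10 and 0.90 to 0.95 for n = 20 when one or two deaths come before all progressions and other censoring. For a single death after the first scan in the illustration, the ratio is 0.83 (n = 10) or 0.92 (n = 20). With no such death there is no effect. The consequence is confined to a secondary descriptive endpoint; PFS, OS and the ORR decision rule are unaffected. It should still be corrected, because one death can be visible in a cohort of 10 and the endpoint cannot be derived both as defined and as tabulated.

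**What to change.** In the TTP paragraph of SAP 10.2, keep Table 5 but replace its death row with two:

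- Death due to the disease under study, without PD: event at the date of death.
- Death from any other cause, without PD: censored at the last adequate assessment, or at treatment start if there is none. This is the date the table already uses for subjects with neither progression nor death.

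Add one sentence that the rows for "No (or inadequate) baseline tumor assessments" and for new anti-cancer therapy, with footnote 3, take precedence over both. State in advance how a missing or unknown cause of death is classified. PFS is not changed; the disagreement between the PFS text and Table 5 on deaths with no post-baseline scan is a separate matter to settle there.

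The cost is two rows and two sentences. No new data are needed: protocol 10.8 has the date and cause of death recorded in the eCRF, and SAP 11.4 already summarizes primary cause of death. The drawback is reliance on the recorded cause of death, which the TTP definition already requires.

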#### **Duration of Response (DOR)**

Duration of response (DOR) is defined as the time from the initial response (CR/PR) to first documented disease progression or death due to any cause, and will be determined only for those subjects from mITT population with a confirmed response (CR or PR). This will be based on investigator assessed response. If a subject has not had an event (disease progression or death), DOR is censored at the date of last adequate tumor assessment. The date of last adequate tumor assessment is the date of the last tumor assessment with overall lesion response of CR, PR or SD before an event or a censoring reason occurred. The date of response at that assessment will be used for censoring.

DOR will be summarized only if there are 5 or more responders from each cohort. Otherwise it will be presented in a listing for all the responders.

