9.8.2.4 Duration of response (DoR)

For the subset of patients with a confirmed CR/PR, DoR is defined as the time from first documented evidence of complete or partial response to the earliest date of disease progression or death due to any cause. For confirmed responders who have not experienced progression or death prior to the date of data cut-off for analysis or starting other anticancer therapy, duration of response will be right-censored on the date of their last adequate post-baseline tumor assessment prior to the cut-off or start of other anticancer therapy.

Duration of response will be summarized descriptively for each cohort using medians and quartiles if there are 5 or more responders (confirmed CR/PR) in one cohort, otherwise, only a listing with subject level details will be provided.

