#### 9.2.5. Imputation of Partial Dates

Only the year of birth is being collected within the EDC system, subject birth date and month will be defaulted to '30/JUN'. For example, if birth year is 1989 then birthdate will be 30/Jun/1989.

With the exception of new anti-cancer start date on the time to event (PFS, TTP, OS) analysis dataset and exposure end date on the Exposure analysis dataset, imputed dates will not be stored on datasets.

Imputed dates will not be displayed in listings. However, where necessary, display macros may impute dates as temporary variables for the purpose of sorting data in listings only. In

addition partial dates may be imputed for 'slotting' data to study time periods (see Section 9.3) or for specific analysis purposes as outlined below.

The partial date imputation will follow ADaM conventions. The ADaM approach is to populate the numeric date variables with the imputed date and add a flag variable to the dataset that indicates the level of imputation.

The flag variable can contain the values: blank, 'D', 'M', 'Y'.

blank: indicates that no imputation was done

D='Day': indicates that the day portion of the date is imputed

M='Month': indicates that the month and day portions of the date are imputed

Y='Year': indicates that the entire date (year, month, and day) is imputed

Example of Date Variables:

XYZD\_ - character date variable

XYZDT - numeric date variable

XYZDTFL - flag variable

Details on imputing partial dates for specific datasets are outlined below.

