#### **Progression-Free Survival (PFS)**

Progression-Free survival (PFS) is defined as the interval between the date of first dose of protocol therapy and the earliest date of disease progression or death due to any cause.

Progression will be based on the investigator assessment. Subjects are considered to have progressive disease if they have documented progression based on radiologic assessment as determined by investigator review (defined in protocol section 10). The date of death should be taken from the Death page in eCRF. Death on study due to any cause will be included. For subjects who do not progress or die, progression-free survival will be censored at the date of last adequate assessment prior to starting new anti-cancer therapy.

If there is no adequate baseline assessment, the subjects will be censored at their treatment start date. Subjects without any adequate post-baseline tumor assessments will also be censored at their treatment start date.

For subjects who receive subsequent anti-cancer therapy the following rules will apply:

- If the start date of the anti-cancer therapy is partial (i.e. either missing the day but has the month and year available or missing both day and month), the imputation rules described in Section 9.2.5.4 will be applied. No imputation will be made for completely missing dates.
- If anti-cancer therapy is started without documented disease progression or is started prior to documented disease progression, then PFS will be censored at the date of the last adequate assessment that is no later than the date of initiation of anti-cancer therapy (i.e. if an assessment occurs on the same day as the start of new anti-cancer therapy the assessment will be used as it will be assumed the assessment occurred prior to the administration of new anti-cancer therapy).
- If a subject has only a baseline visit or does not have an adequate assessment that is no later than the date of initiation of anti-cancer therapy, PFS will be censored at the treatment start date.

If a subject has neither progressed nor died nor started new anti-cancer therapy, then PFS will be censored at the date of the last adequate assessment defined as an assessment where the Investigator determined is CR, or PR, or SD. The date of assessment will be used as the censoring date.

A summary of the assignments for progression and censoring dates for PFS are specified in the following table.

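### The SAP's duration-of-response rule leaves out the protocol's censoring at the start of other anticancer therapy, so a death after a treatment switch is counted as the end of response

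*SAP*

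**What the plan says.** Protocol 9.8.2.4 runs duration of response (DoR) from first documented response to progression or death. It then deals with confirmed responders who reach the data cut-off or start other anticancer therapy before either event: they are "right-censored on the date of their last adequate post-baseline tumor assessment prior to the cut-off or start of other anticancer therapy".

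SAP 10.2 defines DoR as the "time from the initial response (CR/PR) to first documented disease progression or death due to any cause", and the endpoint table in SAP section 2 repeats this. Its censoring sentence is "If a subject has not had an event (disease progression or death), DOR is censored at the date of last adequate tumor assessment". The last adequate assessment is the last one with "overall lesion response of CR, PR or SD before an event or a censoring reason occurred". The SAP does not say what counts as a censoring reason for DoR, and the DoR text does not name new therapy.

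For PFS the SAP does have a rule. When new therapy starts before documented progression, "PFS will be censored at the date of the last adequate assessment that is no later than the date of initiation of anti-cancer therapy", and Table 5 repeats it. TTP takes its event and censoring assignments from that table: they are the "same as that defined in the Table 5 under PFS analysis". DoR has no such cross-reference.

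**The concern.** The two documents treat the same patient differently. A confirmed responder may leave treatment without documented progression (for toxicity, refusal or physician decision; Protocol 8.1), start another therapy and later die. The protocol stops the DoR clock, as censored, at the last adequate scan before the switch. The SAP's text runs it to death and flags an event, so time on the next therapy is credited to pazopanib.

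The follow-up schedule makes this pattern possible. After removal from therapy, Protocol 8.2 collects survival status and later antineoplastic treatment every 3 months. No disease evaluations are scheduled after the end-of-therapy one. Deaths after a switch are recorded; progression after a switch usually would not be.

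The protocol did not leave this point to the SAP. It defers event and censoring details for PFS, OS and TTP to the analysis plan, but states the DoR rule itself. Protocol 9.7.3 requires deviations from the planned analysis to be documented in the analysis plan and the final report, and the SAP records none for DoR.

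**Working it through.** Neither document gives a figure for DoR, so there is none to reproduce. The check compares the rules and then applies them to one assumed patient.

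**1. Rules side by side, for a confirmed responder**

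| Course | Protocol 9.8.2.4 | SAP 10.2 DOR, as written |
|---|---|---|
| Progression, then new therapy | Event at progression | Event at progression |
| New therapy without progression, alive, no later event | Censored at last adequate scan before the switch | Censored; whether scans after the switch count depends on the undefined censoring reason |
| New therapy without progression, then death or later progression | Censored at last adequate scan before the switch | Event at death or later progression |

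The third row is the conflict.

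**2. Inputs for the illustration**

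- Assumed: first response on day 56, later confirmed; last adequate scan on day 112; new therapy afterwards without progression; death on day 200, 300 or 365. Days count from first dose as day 1.
- Days 56 and 112 fit the schedule in Protocol 7.1 (evaluations before Cycles 3 and 5): 2 × 28 = 56 and 4 × 28 = 112.
- From SAP 9.2.4: duration = stop − start + 1; months = days / 30.4375.

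**3. Results**

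- DoR, protocol: 112 − 56 + 1 = 57 days, censored (57 / 30.4375 = 1.87 months).
- PFS, SAP new-therapy rule: 112 − 1 + 1 = 112 days, censored (3.68 months).

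| Death on day | DoR, SAP as written (event) | Months | Excess over protocol value |
|---|---|---|---|
| 200 | 200 − 56 + 1 = 145 days | 4.76 | 145 − 57 = 88 days |
| 300 | 300 − 56 + 1 = 245 days | 8.05 | 245 − 57 = 188 days |
| 365 | 365 − 56 + 1 = 310 days | 10.18 | 310 − 57 = 253 days |

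**4. When DoR exceeds PFS**

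With PFS censored at day 112, DoR is longer when D − 56 + 1 > 112, that is, for death after day 167. If Table 5's row for death without progression is applied instead, PFS is D days and DoR is D − 55 days, so DoR is always shorter. Table 5 does not say which row comes first.

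**5. Chance that a cohort's DoR is summarised at all**

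Both documents summarise DoR only with 5 or more responders and otherwise list it. The binomial P(X ≥ 5) at the design's two response rates is:

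| Cohort size | 5% response rate | 25% response rate |
|---|---|---|
| 10 (stage 1) | 0.00006 | 0.078 |
| 12 (stage 1 plus the two extra rhabdomyosarcoma patients in SAP 4.2) | 0.00018 | 0.158 |
| 20 (both stages) | 0.0026 | 0.585 |

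**6. After the fix**

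The illustrative patient has DoR censored at 57 days, below PFS censored at 112 days, whatever the date of death.

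**The case against.** The best defence is that the SAP's reference to a censoring reason shows that censoring for causes other than reaching the end of data was intended. With the protocol in force and no departure declared, new therapy is the obvious candidate, so this is incomplete drafting. That is probably how it arose, and nothing suggests a deliberate change of rule. It does not cure the text. The phrase only dates the last adequate assessment for subjects without an event, and a responder who switched and died has an event. SAP 9.2 refers derivation details to separate dataset specifications, which are not among the documents and may settle the matter. The SAP should not need them to agree with the protocol.

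The pattern is also narrower than it may seem. An end-of-therapy disease evaluation is due where possible, unless one was done within 2 weeks, so progression present at stopping would usually be recorded.

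Three stronger readings are tempting, and the documents do not support them:

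- **That a cohort median would be distorted.** SAP 4.3 records that the study was declared futile at the end of stage 1. At 10 to 12 patients per cohort, reaching 5 responders is unlikely even at a 25% response rate.
- **That DoR and PFS must contradict each other.** The opening PFS text in SAP 10.2 counts death from any cause and applies censoring to subjects who neither progress nor die. Table 5 makes death without progression an event. The more specific new-therapy rule points to censoring, but no order is stated.
- **That SAP 9.2.5 proves DoR ignores new therapy**, because it refers to the "new anti-cancer start date on the time to event (PFS, TTP, OS) analysis dataset" and omits DoR. That passage concerns where imputed dates are stored. It also lists OS, which is not censored at new therapy, so the list does not show how any endpoint is censored.

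**Conclusion.** The point holds as a conflict between protocol and SAP. Followed literally, SAP 10.2 gives a confirmed responder who switches without documented progression and then dies an event at death. The protocol censors that patient at the last adequate scan before the switch, and no deviation is documented. The value and the event flag are both wrong for such a patient, and the value is too long: by 88 to 253 days in the illustration, which rests on assumed dates.

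The practical reach is small. DoR is a descriptive secondary endpoint, and after a stop at stage 1 the error would show mainly in listed values for individual responders. How many patients would be affected cannot be told from the documents. That DoR would sometimes exceed PFS is conditional on the new-therapy rule outranking the death row in Table 5. The conflict over DoR itself does not depend on that.

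**What to change.** Add to SAP 10.2, Duration of Response: *If new anti-cancer therapy starts before documented progression or death, DOR is censored at the last adequate assessment on or before that start date, and later progression or death is not counted.*

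State the same precedence in Table 5, so that the new-therapy row applies ahead of a later death. This settles PFS, and TTP with it, because TTP uses the same table.

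If the departure from the protocol was intended, document and justify it as Protocol 9.7.3 requires.

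The cost is a short SAP amendment and a small programming change. Start dates of later therapy are already needed for PFS, and later antineoplastic therapies are collected every 3 months. The downside is that DoR may look shorter and more values will be censored.
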